### 3. Genetic Testing N/A

#### A. Describe

- i. the types of future research to be conducted using the materials, specifying if immortalization of cell lines, whole exome or genome sequencing, genome wide association studies, or animal studies are planned
- ii. the plan for the collection of material or the conditions under which material will be received

- iii. the types of information about the donor/individual contributors that will be entered into a database
  - iv. the methods to uphold confidentiality
- B. What are the conditions or procedures for sharing of materials and/or distributing for future research projects?
- C. Is widespread sharing of materials planned?
- D. When and under what conditions will materials be stripped of all identifiers?
- E. Can donor-subjects withdraw their materials at any time, and/or withdraw the identifiers that connect them to their materials?
- i. How will requests to withdraw materials be handled (e.g., material no longer identified: that is, anonymized) or material destroyed)?
- F. Describe the provisions for protection of participant privacy
- G. Describe the methods for the security of storage and sharing of materials

4. **Subject Population:** Provide a detailed description of the types of human subjects who will be recruited into this study.

Participants for patient focus groups will be an estimated 24-30 HIV-infected men and women with a history of tobacco, alcohol or opioid use disorder who receive care in one of the three HIV clinics. These individuals will participate in focus groups to determine their perspective on the optimal ways to integrate treatment for tobacco, alcohol and opioid use disorders into HIV clinics. We will also enroll an estimated 240 staff (clinicians and administrators) across the four sites to participate in focus groups and complete on-line quantitative assessments.

5. **Subject classification:** Check off all classifications of subjects that will be specifically recruited for enrollment in the research project. Will subjects who may require additional safeguards or other considerations be enrolled in the study? If so, identify the population of subjects requiring special safeguards and provide a justification for their involvement.

- |  |  |  |
|--|--|--|
|  Children              |  Healthy                           |  Fetal material, placenta, or dead fetus |
|  Non-English Speaking  |  Prisoners                         |  Economically disadvantaged persons      |
|  Decisionally Impaired |  Employees                         |  Pregnant women and/or fetuses           |
|  Yale Students         |  Females of childbearing potential |  |

NOTE: Is this research proposal designed to enroll children who are wards of the state as potential subjects?  Yes  No (If yes, see Instructions section VII #4 for further requirements)

6. **Inclusion/Exclusion Criteria:** What are the criteria used to determine subject inclusion or exclusion?

**Patient inclusion criteria:**

1. HIV-infected
2. Receiving HIV care in the index clinic
3. Age  $\geq$ 18 years old
4. Meets criteria for lifetime or current tobacco, alcohol and/or opioid use disorder regardless of addiction treatment status
5. Able to provide verbal informed consent

**Staff inclusion criteria:**

1. Employed at participating HIV clinic for at least 6 months
2. Able to provide verbal informed consent.

**Payer inclusion criteria:**

1. Employed at an organization or agency that provides funding for medical services for HIV-infected individuals for at least 6 months.
2. Able to provide verbal informed consent.

**Exclusion criteria:** Unable to provide verbal informed consent

7. How will **eligibility** be determined, and by whom?

**Patients, Staff and Payers:**

Local Research Assistants will recruit patients, staff and payers from their HIV clinical care sites and determine eligibility.

8. **Risks:** Describe the reasonably foreseeable risks, including risks to subject privacy, discomforts, or inconveniences associated with subjects participating in the research.

Risk to subjects is minimal as the intervention proposed is consistent with quality improvement efforts and all analyses will be performed with attention to privacy and security. The participants in the focus groups will be provided with an information sheet outlining the purpose of the study and their ability to opt out at any time. The Site PI or Research Assistant will obtain informed consent from site staff participating in the focus group interviews. The rating scales and questionnaires are all non-invasive, and should also add no risks to subjects, as our past experience indicates.

9. **Minimizing Risks:** Describe the manner in which the above-mentioned risks will be minimized.

Numerous steps will be taken to protect confidentiality. In addition, a Certificate of Confidentiality has been obtained from NIDA to protect information collected from patients during the conduct of the focus groups. This certificate will protect the confidentiality of all patient level data by this study.

**Recruitment and informed consent:**

There are three aspects to the study:

- I. Focus Groups with patients, clinic staff and payers
- II. Online survey based on the measure ORCA – clinic leadership staff and providers
- III. Patient Outcomes: Evaluation of intervention on patient level outcomes using patient-level data from the electronic medical records

## **I. Focus Groups**

Local Research Assistants will recruit patients from their HIV clinical care sites to participate in focus groups. If they are interested, participants will be asked to come to a private office where they will meet with a Research Assistant who will describe the study in more detail, determine interest in participating, and assess potential eligibility. After fully informing participants about the study and answering any questions, the Research Assistant will obtain verbal informed consent.

There may be a perceived risk among HIV clinic staff that participation in this research may impact their employment status in a negative way. To address this concern, we will work with the HIV clinics to provide staff assurances that their participation in the research will in no way affect their employment status either positively or negatively. Surveys and focus groups will be voluntary, and participants will be free to skip any questions they do not wish to answer. Information collected for research purposes will not become part of staff's personnel records. The informed consent for the HIV clinic staff form will outline these assurances. For the recording of the focus group sessions, participants will be made aware during the informed consent process they will be digitally recorded and, for patients, that the nature of these sessions will involve participants speaking about information regarding their health status, smoking, alcohol use, and opioid use, HIV status, and medical history.

Audio recordings will be stored on a password protected computer. The research team and the professional transcriptionists will use the Yale Secure Transfer File website to send recordings and transcripts. Identifying information from any of the participants in the formative evaluations will be kept separately from any forms on which they record information. References to identifying information will be eliminated from the written transcript of the interview in preparation for analysis of qualitative data. Names and any other identifying information collected on evaluation forms, meeting minutes, or field notes and document reviews will be eliminated in preparation for analysis of these records. These precautions are expected to be completely effective in eliminating risks to confidentiality.

**Recorded sessions:** Participants will be made aware during the informed consent process that focus groups will be digitally recorded. However, participants will be instructed to avoid using names and the recordings will be coded by randomly generated group numbers to protect participant confidentiality. Participants will be given the option to have their information redacted from transcripts. The transcripts will be reviewed by [name] or the Research Coordinator and all personally identifying information will be removed prior to analysis. All appropriate actions will be taken by staff members to minimize the risks associated with loss of confidentiality. Audio files will be coded by number and will be erased.

## **II. Online Survey**

**Survey data:** Information obtained from sites will include descriptive information and research assessments. Access to this information will be limited to study staff. Analytic datasets will be created with study identification codes. There will be an online consent for participants.

## **III. Patient Outcomes**

**Electronic medical record data:** We will only collect aggregate and de-identified data from the electronic medical record. Any potentially individual identifiable health information will be protected in accordance with the Health Insurance Portability and Accountability Act (HIPAA) of 1996. All research personnel will be trained on Institutional Review Board (IRB) and HIPAA procedures.

**In Case of Injury:** If a participant is injured as a direct result of participation in this study, treatment will be provided. The participant and/or his or her insurance carrier will be expected to pay the costs of this treatment. No additional financial compensation for injury or lost wages is available. Participants will not waive their legal rights by participating in this study.

**10. Data and Safety Monitoring Plan:** Include an appropriate Data and Safety Monitoring Plan (DSMP) based on the investigator's risk assessment stated below. (Note: the HIC will make the final determination of the risk to subjects.) For more information, see the Instructions, page 24.

- a. What is the investigator's assessment of the overall risk level for subjects participating in this study? **Minimal**
- b. If children are involved, what is the investigator's assessment of the overall risk level for the children participating in this study? N/A
- c. Include an appropriate Data and Safety Monitoring Plan. Examples of DSMPs are available here <http://www.yale.edu/hrpp/forms-templates/biomedical.html> for
  - i. Minimal risk
  - ii. Greater than minimal

### **Data and Safety Monitoring Plan:**

The risk of loss of privacy is minimal. Measures in place to prevent the loss of privacy include password protection on data files and computer workstations.

Below we detail the data center architecture, backup strategies, and physical data storage that will support the protection of our data.

### **Data Monitoring and Storage:**

We are planning to use a Web-based computer system for data collection, monitoring and reporting. This system has proven to be very efficient and reliable in clinical trials being conducted by our research team. The core of this system consists of a database hosted on a network of secure servers that are capable of collecting and storing data using Web based applications that are accessed by the remote users via standard Internet browsers. The Web based

data system is designed to fulfill strict requirements of a clinical trial regarding data collection, monitoring, and reporting from the recruitment of participants to the delivery of data sets suitable for statistical analyses at the end of the trial. The system meets the highest security and reliability standards. All connections to the systems are secured and encrypted and only authorized users are able to access the system. All data is stored in encrypted files, and multiple backups of the system and all data are maintained.

Data and safety monitoring procedures in this study include computerized data collection and monitoring systems and an organizational structure of clearly defined tasks assigned to all research and clinical personnel involved in the conduct of this study. The computerized data collection and monitoring system consists of a database system that records research activities, completion of scheduled assessments, and delivers computerized versions of most of research instruments used in this study. Research assistants use this database to monitor and schedule activities and to administer study assessments. Data entry of non-computerized assessments is accomplished by using specialized data entry software (such as, SPSS Data Entry or Microsoft Access Data base) facilitating efficient data entry and allowing elimination of out-of range values and double entry of data for detection of key punch errors.

The organizational structure used to ensure quality of data in this project include: 1) extensive training and close supervision of research assistants in data collection; 2) preliminary review of all data for completeness and coding errors by data manager/analyst; and 3) utilization of error-checking statistical procedures.

Experienced data manager/analysts and the PI supervise data procedures. The research team will meet weekly to review the overall progress of the study. All error corrections are fully documented in the research records of the study. All research personnel are required to participate in and document training in protection of human subjects and the responsible conduct of scientific research. Procedures for training and supervision of Research Assistants, and transcriptionists have been developed as part of our previous and current studies. Initial training utilizes intensive seminars on all of the research instruments, after which the coordinator observes the trainer administer the assessments and co-rates the assessments. Subsequently, the coordinator will conduct the assessments and make the ratings with the trainer present for a minimum of five full assessments and until complete agreement is obtained. During the study, the Yale-based Research Coordinator will review all survey assessments and provide feedback on the completeness, accuracy or errors forms. Continued supervision and training on all instruments is provided on a regular basis to insure continued reliability of the assessments.

- d. For multi-site studies for which the Yale PI serves as the lead investigator:
  - i. How will adverse events and unanticipated problems involving risks to subjects or others be reported, reviewed and managed?

All adverse events are reported using the Yale Institutional Review Board (IRB) standard template for reporting adverse events. The Yale Principal Investigator (PI) reviews all adverse events, classifies the attribution of adverse events (e.g., definitely, probably, possibly related; unlikely or unrelated) and grades the severity of the event, utilizing the FDA's definition of serious adverse events, on a 6-point scale (0=no adverse event or within normal limit; 1=mild; 2=moderate; 3=severe; 4=life-threatening; 5=fatal). Serious, definitely protocol related adverse events will be

reported immediately to the IRB and to NIDA. Adverse events will be reported in summary form at least annually to the IRB. The summary will include the number of subjects enrolled and a summary of graded adverse events to date, using the chart format included in the Yale University DSMP template. The PI will evaluate all adverse events and determine whether the event affects the Risk/Benefit ratio of the study and whether modifications to the protocol (e.g., Risks to Subjects) or consent form (e.g., Risks and Inconveniences) are required.

- ii. What provisions are in place for management of interim results?

No interim analyses will be performed.

- iii. What will the multi-site process be for protocol modifications?

There will be one protocol document and each participating institution will utilize that document. The Yale PI is responsible for the coordination of the approval of the protocol as well as its subsequent amendments and will be responsible to ensure that the sites are using the correct version of the protocol. The Yale PI will collect and maintain copies of all IRB approvals from each site and will collect and review conflicts of interest declarations made by the Site PIs.

**11. Statistical Considerations:** Describe the statistical analyses that support the study design.

**General considerations:** This is a stepped wedge randomized trial to evaluate the impact of Implementation Facilitation. Randomization and data analysis will be conducted by Drs. [name], [name] and the Yale Center for Analytic Sciences (YCAS). All analyses will be carried out using SAS v9.3 (SAS Institute, Cary, NC) and an alpha level of 0.05 will be used to establish statistical significance.

**Interim monitoring:** Interim monitoring will focus on adherence to protocol, completeness of data retrieval from each clinics electronic medical record, and uptake of the Implementation Facilitation. A set of monitoring tables will be generated by YCAS for this purpose. No interim looks for efficacy are planned.

**Analysis for Aim 2a, 2b, and 2c:** Number (percent) will be used to present data from categorical variables. Continuous variable data will be presented as means (+/- SD) and those with a non-normal distribution will be characterized using medians (interquartile range). Differences across the clinics will be assessed using appropriate parametric or non-parametric techniques. The provision of addiction treatments among those eligible (Aim 2c) will be expressed as a percentage and the distribution of results in the control (unexposed) periods will be compared with those in the evaluation (exposed) and maintenance (exposed) periods. Characteristics of patients and clinics will be shown by randomization status in each step of the design. We will conduct similar analyses for the measures of organizational and provider readiness (Aims 2a, 2b) where the dependent variable will be expressed as continuous measures (ORCA score and change rulers). Based on the PARIHS, we hypothesize that stakeholder scores on the ORCA subscales including clinical experiences, patient preferences, leadership culture

and measurement will mediate the proportion of patients receiving addiction treatment. We will test the relationship among this outcome and these mediators. To test the significance of the mediation effect, which is called the indirect effect, we will calculate Sobel's test for each proposed mediator. We will use an intent-to-treat approach (i.e. cluster analysis will be done) according to the time clinics were intended to cross over from control to Implementation Facilitation. A linear mixed model will be used, adjusting for calendar time (a potential confounder due to its association with both exposure to the intervention and outcome), with a random effect for clinic, a fixed effect for each step and allowing for repeated measures for patients in the clinics. Since the population of the clinics participating in the proposed trial will be rather stable, thus rendering this a cohort stepped wedge design, an additional random effect for patients in each clinic will be introduced.

**Analysis for Aim 2d:** To determine the impact of Implementation Facilitation on models of care we will describe the extent to which the provision of treatment for each substance is coordinated (facilitated by the HIV clinic), co-located (provided in the clinic) or integrated (provided by the primary HIV provider) by clinic. We will track changes in these models of care from the control period to the evaluation and maintenance periods.

**Analysis for Aim 3:** These analyses will be restricted to patients diagnosed with a tobacco, alcohol or opioid use disorder. ART receipt will be defined as at least 180 days of three concurrent antiretroviral agents in the 6-month interval based on prescriptions in the electronic medical record. Viral suppression, will be defined as HIV RNA <200 copies/mL at last test closest to the time of data extraction, consistent with Department of Health and Human Services (DHHS) guidelines. Although current limits of detection are lower, this cutoff allows for low-level “blips” that have no clinical significance. The VACS Index will be evaluated based on most recent values at the time of data extraction. VACS Index score will be treated as a continuous variable. Retention in HIV care, per DHHS guidelines uses a 24-month measurement period. It is defined as at least one HIV medical care visit in each 6-month period, with a minimum of 60 days between the first medical visit in the prior 6-month period and the last medical visit in the subsequent 6-month period. This measure has good agreement with the Institute of Medicine indicator for retention in care and is an independent predictor of mortality. We will evaluate whether patients have had at least 1 visit in the 6-month period prior to time of data extraction. These analyses will be adjusted for demographics (age, gender), and presence of psychiatric diagnosis (anxiety, major depression, severe mental illness). We will use descriptive statistics to characterize addiction treatment eligible patients overall and by substance at baseline and examine changes at each interval. We will then examine each of these HIV-related outcomes at the 6-month intervals of control, evaluation and maintenance phases based on the provision of addiction treatment. We will determine the association between provision of addiction treatment, including benzodiazepines and outcomes with the MIXED models procedure repeated measures and generalized estimating equations (GEE) to account for repeated measures for dichotomous outcomes. We will adjust for fixed demographics, substance use disorder and psychiatric diagnoses. We will describe the association with odds ratios and 95% confidence intervals. For continuous outcomes, we will use multivariable linear regression with GEE with similar adjustment.

**Plan for Missing Data:** Several strategies will be imposed to accommodate the likelihood that missing data will occur during this study. Prevention is the most obvious and effective manner to control bias and loss of power from missing data. We will follow the intent to treat principle, requiring follow-up of all clinics randomized regardless of the treatment received. Timely data entry combined with quarterly missing data reports will trigger protocols for tracking and obtaining missing data. Despite these efforts it is reasonable to assume missing data will occur. Our primary analysis is valid under the assumption that missing data is missing at random (MAR). We will evaluate the plausibility of this assumption by determining the extent of missing data and use logistic regression to identify factors associated with missing data. We will conduct sensitivity analysis using pattern-mixture and selection models under missing not at random (MNAR) assumptions to examine the robustness of conclusions of the primary analysis to missing data.

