## **Implementation Facilitation leads to practice change**

Defined as a “process of ‘helping individuals and teams to understand what they need to change and how they need to change it in order to apply evidence to practice,’” Implementation Facilitation is an effective intervention that includes a “deliberate process of interactive problem solving and support that occurs in the context of a recognized need for improvement and supportive interpersonal relationship.” (Table 2)

**Research Plan:** Summarize the study design and research procedures using non-technical language that can be readily understood by someone outside the discipline. **Be sure to distinguish between standard of care vs. research procedures when applicable, and include any flowcharts of visits specifying their individual times and lengths.** Describe the setting in which the research will take place.

The **Working with HIV clinics to adopt Addiction Treatments using Implementation Facilitation (WHAT IF?)** study will evaluate the impact of Implementation Facilitation on the adoption of addiction treatment services in four HIV clinics. We will use a stepped wedge design (See Table 4). The stepped wedge design is a variation on a cluster randomized clinical trial in which participating sites are randomly assigned a time at which the intervention (Implementation Facilitation) is begun. The primary comparison is of the change that occurs from the pre-implementation period to two post-implementation periods, the initial six months (evaluation) and the following six months (maintenance). This proposal will consist of three main components in each of four clinics: 1) **formative evaluation** with key stakeholders at each site to guide and refine the Implementation Facilitation, 2) **conduct of the Implementation Facilitation** and 3) an **evaluation of the impact** of the Implementation Facilitation on organization and provider-level readiness, provision of addiction treatments, and HIV outcomes.

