### **Evaluating the Effectiveness of the Implementation Facilitation (Aim 2 and Aim 3)**

#### Overview

We will use a stepped wedge design (Table 4) to evaluate the effect of the Implementation Facilitation on the outcomes. In a stepped wedge design, clinics are randomly assigned to time cohorts and then followed prospectively to determine their outcome status. Stepped wedge designs are increasingly used to promote the implementation of evidence-based practice and are appropriate for evaluating interventions where there is evidence that the intervention is likely to be beneficial and when practical considerations require sequential deployment of an intervention. We will have three phases of six-months each: 1) a pre-implementation control period, 2) a post-intervention evaluation period, and 3) a maintenance period. The proportion of eligible patients in each time period who receive at least one addiction treatment will be assessed and the effect of the intervention will be evaluated by comparing pre-implementation to evaluation and maintenance periods. This will allow us to assess the short and long-term (maintenance) impact of Implementation Facilitation.

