**Table 4. Overview of clinic phases the stepped wedge study design (IF = Implementation Facilitation)**

Clinic 1	Control	Control	Control	Control	IF	Evaluation	Maintenance
Clinic 2	Control	Control	Control	IF	Evaluation	Maintenance	Maintenance
Clinic 3	Control	Control	IF	Evaluation	Maintenance	Maintenance	Maintenance
Clinic 4	Control	IF	Evaluation	Maintenance	Maintenance	Maintenance	Maintenance

We will measure a range of implementation variables at baseline, 6 and 12 months (Table 5). Using validated instruments before, during and after Implementation Facilitation we will examine the impact of Implementation Facilitation on organization readiness, provider readiness, treatment provision, models of care and HIV outcomes. For sample size calculation, the primary quantitative outcome, assessed six and 12 months after the Implementation Facilitation is completed, will be the proportion of eligible individuals receiving addiction treatments from the clinic measured using information derived from the electronic medical record. This determination will be conducted in a blinded fashion, such that the individual analyzing the electronic medical record data will be unaware of the phase (control, evaluation, maintenance) of the Implementation Facilitation. Secondary quantitative outcomes, assessed at six and 12 months will be change in organizational readiness measured using the ORCA, change in provider readiness to prescribe addiction medications measured using change rulers, and HIV-related outcomes. To facilitate data collection, all surveys will be administered to all stakeholders online using the survey software, Qualtrics and collected anonymously.

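### The periods in the primary analysis are not settled, the model lets no clinic drift from the common time course, four clinics get no small-sample method, and two primary contrasts share one alpha

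*Combined protocol and SAP*

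**What the plan says.** **Periods.** Section V, Research Plan: "The primary comparison is of the change that occurs from the pre-implementation period to two post-implementation periods", that is, the first six months after implementation and the six after that. The Overview of the effectiveness evaluation: "We will have three phases of six-months each" (control, evaluation, maintenance). Table 4, "Overview of clinic phases the stepped wedge study design", has seven columns per clinic: one to four control, one IF, one evaluation and one to four maintenance. The text below it: "We will measure a range of implementation variables at baseline, 6 and 12 months". Adequacy of sample size speaks of three main time points, but its inputs are b = 1, k = 4 and t = 1, which means five measurement periods.

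**Model** (Section V, item 11, Analysis for Aim 2a, 2b, and 2c). A linear mixed model adjusted for calendar time, "with a random effect for clinic, a fixed effect for each step and allowing for repeated measures for patients in the clinics". Because the clinic populations are taken to be stable, "an additional random effect for patients in each clinic will be introduced". For treatment provision, "the distribution of results in the control (unexposed) periods will be compared with those in the evaluation (exposed) and maintenance (exposed) periods". The same paragraph sets the intent-to-treat crossover at the move from control into IF, yet IF is not among the periods labelled exposed. The IF column is therefore given no role.

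**Testing.** Item 11, General considerations: "an alpha level of 0.05 will be used to establish statistical significance". No section names a clinic-by-step effect, a degrees-of-freedom rule, a permutation test or any other provision for four clusters. None gives an order, split or joint test for the two contrasts.

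**The concern.** Random effects for clinic and patient, with step effects common to all clinics, mean that a clinic may sit higher or lower than the others but must follow the same time course. If one clinic moves by itself from one six-month period to the next, the model counts that movement as patient-level noise. With hundreds of patients per clinic-period that noise looks small, so the standard error of the evaluation and maintenance contrasts would be too small.

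Whether this matters depends on the period layout. With many periods per clinic, the contrast is largely a within-clinic one and the missing term is exposed. With three periods per clinic, it depends on comparing the four clinics with each other, and the missing small-sample method becomes the weak point. Separately, two contrasts that both count as primary, each tested at 0.05, give more than a 5% chance of at least one false positive even when the model is right.

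**Working it through.** **1. The plan's own figures.** For 15% against 26%, two-sided alpha 0.05 and 90% power, the two-proportion formula gives 281 per arm without and 299 with continuity correction; the plan has 296 (592 in total). The Woertman design effect with n = 300, rho = 0.01, k = 4, b = 1, t = 1 is

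[1 + 0.01(1200 + 300 − 1)] / [1 + 0.01(600 + 300 − 1)] × 3(0.99) / [2(4 − 1/4)] = (15.99 / 9.99) × 0.396 = 0.634.

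Then 592 × 0.634 = 375, and 375 / 4 = 94 per clinic. These inputs describe b + kt = 1 + 4 = 5 periods, which is neither Table 4 nor the three time points.

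**2. Possible layouts.**
- All control, evaluation and maintenance cells of Table 4: 28 − 4 IF = 24 cells.
- One maintenance period per clinic: 10 + 4 + 4 = 18 cells.
- Last control, evaluation and first maintenance: 12 cells. With fixed clinic, step and phase effects the design has rank 11 of 12. Calendar period equals clinic start plus a fixed offset, so within-clinic data cannot separate the phase effects from a linear time trend. Estimation then depends on comparisons between four clinics.
- Control taken only from the first Table 4 column, one reading of baseline: 12 cells. Every later step contains only evaluation or maintenance cells, so the two phase indicators add up to the later step indicators. Rank is 7 of 8 even with a random clinic effect, and neither contrast with control can be estimated.

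**3. Effect of the missing term.** From the plan: ICC 0.01 and p = 0.15. Assumed, because the documents give none: the cluster autocorrelation (CAC), the correlation of a clinic's effect between periods. The clinic variance is 0.01 × 0.15 × 0.85 = 0.001275. The clinic-specific period SD is √[(1 − CAC) × 0.001275], which is 1.1 percentage points at CAC 0.9 and 2.5 at 0.5. Sampling variance of a cell at 300 patients is 0.99 × 0.1275 / 300 = 0.000421.

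The SE ratio (true to modelled) is close to √[1 + (1 − CAC) × 0.001275 / 0.000421], or 1.14, 1.27 and 1.59 at CAC 0.9, 0.8 and 0.5. The exact generalised least squares values on 24 cells are 1.14, 1.26 and 1.57. Type I error is 2[1 − Φ(1.96 / ratio)].

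Evaluation contrast, IF excluded, independent patients, variances known:

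| Layout | Patients per clinic | CAC 1 | 0.9 | 0.8 | 0.5 |
|---|---|---|---|---|---|
| 24 cells | 300 | 5.0% | 8.5% | 12% | 21% |
| 24 cells | 94 | 5% | 6% | 7% | 10% |
| 18 cells | 300 | 5.0% | 8.2% | 11% | 20% |
| 12 cells, last control | 300 | 5.0% | 5.2% | 5.3% | 5.8% |

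With an assumed within-patient correlation of 0.5 (24 cells, 300 per clinic) the errors are 5, 12, 19 and 33%.

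**4. Small-sample method.** By simulation (10,000 runs per scenario), adding only Kenward-Roger to the planned model on 24 cells at 300 leaves 5.1, 8.6, 12.1 and 20.9%. On 12 cells with last control, the clinic variance estimated and a normal reference (an assumption), the error is 13 to 15% at 300 and 8 to 9% at 94, already at CAC 1.

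**5. IF coding.** At 94 per clinic and CAC 1, the evaluation SE is 0.037 with IF excluded and 0.027 with IF counted as control or as exposed. At 300 it is 0.021 against about 0.016. The coding hardly changes the type I errors in step 3, but it changes precision and so power.

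**6. Two contrasts.** On 24 cells the two estimates correlate at 0.80 to 0.81. From the bivariate normal, the family-wise error with both tested at 0.05 and the model right is 7.8%. On 12 cells it is 6.8 to 7.5%.

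**The case against.** The documents give no between-period correlation. At CAC 1 the planned model is correct and the missing term does no harm, so the 8.5 to 21% is a sensitivity range and not a finding about these clinics. This stands. A reader might infer that the trial's standard errors are wrong. The documents do not show that clinics drift apart; they show only that the model assumes they do not.

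The analysis text fits Table 4 better than the three-period reading: it speaks of control periods in the plural, adjusts for calendar time and has a step effect. The three time points may simply name the three phases. This also stands, so the 13 to 15% error is not the expected result; it needs the weaker reading, the last control period and a normal reference. The contradiction still needs resolving, because the sample size, Table 4 and the assessment times cannot all describe one dataset.

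The sample size is based on the evaluation contrast, and both contrasts concern one outcome in the short and longer term. That hints at an order, but the Research Plan makes both comparisons primary and no order is written. Separate tests at 0.05 are the plain reading, not literal text.

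Finally, 94 per clinic is the calculated requirement; the plan assumes at least 300 eligible patients per clinic. A reader might conclude from the results at 94 that the trial is underpowered. The documents do not support that if 300 is achieved.

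**Conclusion.** The point holds in conditional form. Three things are certain from the text: the period descriptions conflict and the IF column has no role; the primary model has no clinic-by-step effect and no method for four clusters; and two primary contrasts share one alpha without an order.

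The size of the harm depends on what is not stated. On the Table 4 layout it ranges from none at CAC 1 to about 21% at CAC 0.5, and a clinic-specific SD of 1.1 points per period is enough for 8.5%. This assumes ICC 0.01, 300 per clinic, independent patients and IF excluded. On three periods per clinic the missing term is nearly harmless, but the contrasts either depend on four clinics or cannot be estimated. The family-wise excess is modest, about 7 to 8% instead of 5%. This should be corrected before analysis; confidence in the size is medium.

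**What to change.** 1. Reconcile Table 4 with the Overview, the sample-size section and the crossover wording in item 11. Use all control, evaluation and maintenance periods. State whether IF is excluded, control or exposed, with another coding as a sensitivity analysis.
2. Add a random clinic-by-step effect with Kenward-Roger degrees of freedom. In simulation on 24 cells this gives an error of 3.5 to 5.3% for evaluation and 3.4 to 6.0% for maintenance. The added variance is estimated at zero in up to 56% of runs, so also report an analysis of clinic-period proportions with fixed clinic and step effects (24 − 12 = 12 residual df; evaluation error 4.3 to 5.3%).
3. Test evaluation at 0.05, then maintenance at 0.05 only if evaluation is significant. Holm is the alternative if both matter equally. Report both intervals in any case.
4. Restate power for the chosen layout, IF coding and model.

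**Cost.** Intervals widen, and more record extracts than the three in Table 5 may be needed, though from routine-care records. On 24 cells with IF excluded and independent patients, evaluation power at CAC 1, 0.9, 0.8 and 0.5 is 98, 96, 93 and 83% at 300 per clinic, and 63, 61, 59 and 55% at 94. If the added term is not needed (CAC 1), it lowers power from 99 to 98% at 300 and from 72 to 63% at 94. The 12-cell layout with last control gives only 44 to 46% at 300. At CAC 0.9 the fixed order lowers maintenance power (33% against 15%) from 100 to 96% at 300 and from 81 to 59% at 94. Holm gives 96% for evaluation and 99% for maintenance at 300, and 58% and 72% at 94.
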